9.1 Study Drug Exposure

Study drug exposure data will be integrated, listed, and summarized for the Safety population.

Duration of exposure will be summarized by treatment/analysis group and is defined as:

Duration of exposure (Days) = (Date of Last Dose – Analysis Day 1) + 1.

9.2 Adverse Events

An adverse event (AE) is any untoward medical occurrence that occurs in conjunction with the use of a medicinal product in humans, whether or not considered to have a causal relationship to the medicinal product. An AE can, therefore, be any unfavorable or unintended sign (including a clinically significant abnormal laboratory finding), symptom, or disease

temporally associated with the use of a medicinal product, whether or not considered related to the medicinal product.

Adverse event data will be integrated, listed, and summarized for the Safety population. Events will be presented according to MedDRA® system organ class (SOC) and preferred term (PT). Summaries will be ordered alphabetically by SOC and PT, and by decreasing frequency of preferred term among all treatment/analysis groups regardless of whether a "total" column is presented.

Partial (Incomplete) AE onset and end dates will be listed as such. All AEs collected on the AE eCRF page will be considered treatment–emergent.

Most commonly reported (at least 2% of either active or placebo treatments) AEs will be presented by preferred term, and summarized by treatment/analysis group.

For each summary, at each of the SOC and PT levels, a subject will be counted once if he/she reported one or more AEs. Percentages will be calculated out of the number of subjects in the Safety population.

9.2.1 Incidence of Adverse Events

Adverse events will be summarized by treatment/analysis group, SOC and PT.

9.2.2 Causality of Adverse Events due to Study Drug

The investigator will use clinical judgment to assess the causality of each AE/Serious Adverse Event (SAE) due to study drug based on pre-defined criteria. Adverse events will be summarized by this causality.

In the statistical analyses, if a subject experiences multiple occurrences of the same SOC or PT, only the related occurrence (if any exists) will be summarized. If the causality due to the study drug is missing, it will be considered "related". The imputed values for causality due to study drug will be used for the incidence summary while actual values will be listed.

9.2.3 Intensity of Adverse Events

Adverse events will be summarized by treatment/analysis group and intensity. In this summary, if a subject reported multiple occurrences of the same AE, only the most intense AE will be presented. AEs with missing intensity will not be included in the summary table, but will be presented in the data listing with a missing intensity.

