5.1 Safety

The Safety population will include all subjects who received at least one dose of study drug. It will be used for all safety analyses.

6 General Considerations for Statistical Analyses

Analysis Dataset Model (ADaM) datasets will be in accordance with the Clinical Data Interchange Standards Consortium (CDISC) standards and will be derived from the individual study data tabulation model (SDTM) and ADaM datasets for each study.

All tables, listings, figures and any other supportive SAS output will include in the footer explanatory notes that will indicate, at a minimum, the programming source (i.e., name, file path of the SAS program that generates the output), and run date.

Continuous data will be described using descriptive statistics as follows: number of observations (n), mean, median, standard deviation, minimum, and maximum, unless otherwise specified. All minimum and maximum values will be displayed with the same number of decimal places relative to the raw data, the mean and median will be displayed with one additional decimal place, and the standard deviation will be displayed with two additional decimal places.

Categorical data will be summarized by the number and percentage of subjects in each category. The denominator of all percentages will be the number of subjects in the population of interest, unless otherwise stated. When count data are presented, the percent will be suppressed when the count is zero in order to draw attention to the non-zero counts. A row denoted "Missing" will be included in count tabulations where necessary to account for dropouts and missing values. Non-zero percentages will be rounded to one decimal place, except 100% will be displayed without any decimal places.

In summary tables for categorical data, all categories will be presented if they are specified on the Case Report Form (CRF), or if categories are ordered intervals (e.g., age groups), regardless of whether data were present in each category, unless otherwise specified. For other categorical data (e.g., AEs and medications), only categories with non-zero frequencies will be presented.

Data will be displayed in all listings sorted by subject, study ID, and treatment. All summaries will be presented by treatment/analysis group, unless otherwise specified.

When no data are available for a table or appendix, an empty page with the title will be produced with suitable text (e.g., "There are no observations for this table/appendix.").

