Note: A subject is counted once within each preferred term. Percentages are calculated out of the number of subjects in the active treatment/analysis group. AEs are coded using MedDRA Version 17.0. Source Data: Listing 2.6.1

<DIRECTORY PATH>PROGRAM NAME Executed: DDMMMYYYY hh:mm

Programming Note: Sort by descending frequency in ADS-5102 treatment group

Same display as 1.6.2.1

Note: A subject is counted once within each preferred term. Percentages are calculated out of the number of subjects in each treatment/analysis group. AEs are coded using MedDRA Version 17.0.

Source Data: Listing 2.6.1

Table 1.6.5

Adverse Events by Highest Intensity, System Organ Class and Preferred Term Safety Population

Treatment: Placebo

System Organ Class	(N=xx) n (%)				
Preferred Term	Mild	Moderate	Severe	Total	
Number (%) of subjects with any AEs	xx (xx.x)	xx (xx.x)	xx (xx.x)	xx (xx.x)	
System Organ Class 1	xx (xx.x)	xx (xx.x)	xx (xx.x)	xx (xx.x)	
Preferred Term 1	xx (xx.x)	xx (xx.x)	xx (xx.x)	xx (xx.x)	
Preferred Term 2	xx (xx.x)	xx (xx.x)	xx (xx.x)	xx (xx.x)	
Preferred Term 3	xx (xx.x)	xx (xx.x)	xx (xx.x)	xx (xx.x)	
System Organ Class 2	xx (xx.x)	xx (xx.x)	xx (xx.x)	xx (xx.x)	
Preferred Term 1	xx (xx.x)	xx (xx.x)	xx (xx.x)	xx (xx.x)	
Preferred Term 2	xx (xx.x)	xx (xx.x)	xx (xx.x)	xx (xx.x)	
Preferred Term 3	xx (xx.x)	xx (xx.x)	xx (xx.x)	xx (xx.x)	

Note: A subject is counted once within each preferred term and system organ class. Percentages are calculated out of the number of subjects in each treatment/analysis group. AEs are coded using MedDRA Version 17.0.

Source Data: Listing 2.6.1

Treatment: 340mg ADS-5102

System Organ Class	(N=xx) n (%)				
Preferred Term	Mild	Moderate	Severe	Total	
Number (%) of subjects with any AEs	xx (xx.x)	xx (xx.x)	xx (xx.x)	xx (xx.x)	
System Organ Class 1	xx (xx.x)	xx (xx.x)	xx (xx.x)	xx (xx.x)	
Preferred Term 1	xx (xx.x)	xx (xx.x)	xx (xx.x)	xx (xx.x)	
Preferred Term 2	xx (xx.x)	xx (xx.x)	xx (xx.x)	xx (xx.x)	
Preferred Term 3	xx (xx.x)	xx (xx.x)	xx (xx.x)	xx (xx.x)	
System Organ Class 2	xx (xx.x)	xx (xx.x)	xx (xx.x)	xx (xx.x)	
Preferred Term 1	xx (xx.x)	xx (xx.x)	xx (xx.x)	xx (xx.x)	
Preferred Term 2	xx (xx.x)	xx (xx.x)	xx (xx.x)	xx (xx.x)	
Preferred Term 3	xx (xx.x)	xx (xx.x)	xx (xx.x)	xx (xx.x)	

Note: A subject is counted once within each preferred term and system organ class. Percentages are calculated out of the number of subjects in each treatment/analysis group. AEs are coded using MedDRA Version 17.0.

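### SAP 9.2.3 drops ungraded adverse events from the intensity summary, so the Total in Table 1.6.5 can fall below the number of subjects with an AE; a Missing category would correct it

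*SAP*

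**What the plan says.** SAP Section 9.2.3 (Intensity of Adverse Events) gives two rules. For repeated events, "if a subject reported multiple occurrences of the same AE, only the most intense AE will be presented". For ungraded events, "AEs with missing intensity will not be included in the summary table"; they appear only in the data listing, with the intensity shown as missing.

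The table concerned is Table 1.6.5, "Adverse Events by Highest Intensity, System Organ Class and Preferred Term Safety Population". Its shell has columns for Mild, Moderate, Severe and Total, and its first row is for subjects with any AE. The footnote takes percentages over all subjects in the treatment/analysis group. It does not define Total and does not mention the exclusion. There is no Missing column.

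Three other parts of the SAP bear on this:

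- Section 9.2 (Adverse Events) sets the general counting rule: "For each summary, at each of the SOC and PT levels, a subject will be counted once if he/she reported one or more AEs".
- Section 6 (General Considerations for Statistical Analyses) says that a row labelled Missing "will be included in count tabulations where necessary to account for dropouts and missing values".
- Section 9.2.2 (Causality) fills in missing values: "If the causality due to the study drug is missing, it will be considered" related. It adds that "The imputed values for causality due to study drug will be used for the incidence summary while actual values will be listed".

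Table 1.6.1.1, the AE overview, also breaks subjects down by highest intensity, once for all AEs and once for drug-related AEs. Both blocks have Mild, Moderate and Severe rows only.

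**The concern.** Table 1.6.5 presents itself as a count of subjects with AEs, split by their worst grade. Under Section 9.2.3 it counts only subjects with at least one graded AE. The denominator still includes everyone, so an excluded subject is shown in effect as having had no event.

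Two tables in the same report could then give different numbers on rows with the same label, with nothing in the footnotes to explain it. SAP Section 9 plans no formal testing, so these descriptive counts are themselves the safety result, and they should reconcile.

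**Working it through.** The plan states no figure on this point, so there is none to reproduce. The check applies the rule by direct count and then asks how large the effect could be.

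**Direct count.** Take six subjects in one group, with these AE intensities:

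| Subject | AE intensities | Table 1.6.5 under Section 9.2.3 | With a Missing category |
|---|---|---|---|
| 1 | mild | Mild | Mild |
| 2 | moderate, missing | Moderate | Moderate |
| 3 | missing | not counted | Missing |
| 4 | severe | Severe | Severe |
| 5 | missing, missing | not counted | Missing |
| 6 | no AE | none | none |

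- Section 9.2.3 as written: Total = 1 + 1 + 1 = 3, shown as 3/6 = 50.0%.
- Counting rule of Section 9.2, as used in Table 1.6.2.1: 5 subjects with any AE, shown as 5/6 = 83.3%.
- With a Missing category: 1 + 1 + 1 + 2 = 5, which agrees with Table 1.6.2.1.

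Subject 2 stays in the Total but is classed on the graded record alone, so the true highest intensity may be understated.

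**The overview table.** The same two ungraded subjects are in the AE row of Table 1.6.1.1 but can be in none of its three intensity rows, so 3 does not add up to 5. In the drug-related block, an AE lacking both causality and intensity is counted as related under Section 9.2.2 and then has no intensity row to go in. The SAP does not say whether the summary table named in Section 9.2.3 includes Table 1.6.1.1, but the shell leaves no place for these subjects either way.

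**Scale.** The documents give no rate of missing intensity, so the rate m is an assumption, shown over a range. Suppose each AE record lacks intensity independently with probability m, and each subject has k AE records at the level considered. A subject is lost only if all k are ungraded, which has probability m^k. Among 100 subjects with an AE, the expected loss is 100 × m^k, and the chance of losing at least one is 1 − (1 − m^k)^100.

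| m | k = 1: expected loss; chance of at least one | k = 2: expected loss; chance of at least one |
|---|---|---|
| 0.5% | 0.5; 0.394 | 0.003; 0.002 |
| 1% | 1; 0.634 | 0.01; 0.010 |
| 2% | 2; 0.867 | 0.04; 0.039 |
| 5% | 5; 0.994 | 0.25; 0.221 |

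With k = 5 both figures are zero to three decimals throughout. The exposure is therefore mainly at preferred-term level, where a subject often has a single record, and it is slight in the any-AE row.

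**One subject's weight.** Placebo subjects come only from the two randomised studies. Assuming exact allocation and that all were dosed, N is about 83/4 + 126/2 = 83.75, or 84. One lost subject is then 1/84 = 1.2 percentage points. In a group of 250, taken for illustration, it is 1/250 = 0.4 points.

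**The case against.** Several objections are sound, and they limit the point.

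- **Missing grades should be rare.** Protocol Section 12.1.1 lists severity among the attributes that must be assigned to each AE, and Section 14.4 requires the investigator to sign off all eCRFs. This stands, although it is the protocol of ADS-AMT-PD302 only; the protocols of the other two integrated studies are not available here.
- **The overall AE count is not lost.** The any-AE rows of Tables 1.6.1.1 and 1.6.2.1 do not depend on intensity, and the ungraded events remain in the listing. This stands; the problem is confined to the intensity breakdown.
- **Section 6 is discretionary.** It asks for a Missing row where necessary, and a specific rule may depart from a general default. This is fair. The firmer conflict is with Section 9.2, whose counting rule covers each summary.
- **Total is undefined.** A programmer could fill it with all subjects who had an AE. That would avoid the mismatch but would contradict the wording of Section 9.2.3, and the three grades would then not add up to the Total.

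A reader might also infer that the rule contradicts the worst-case handling of causality. It does not: causality and intensity are different variables, and nothing requires the same missing-data rule for both. The contrast shows uneven handling, but it does not cause the shortfall.

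**Conclusion.** Followed as written, Section 9.2.3 can make the Total in Table 1.6.5 smaller than the number of subjects with an AE at the same level in Table 1.6.2.1, contrary to Section 9.2. It can also leave the intensity rows of Table 1.6.1.1 short of their AE rows. This is a possibility and not a certainty: it needs a subject with no graded AE at that level. The effect is probably very small, and it cannot be sized further without a missing rate.

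A reader might infer that the exclusion always flatters ADS-5102. The documents do not support that. The rule applies to placebo as well, and losing a placebo subject makes the drug look worse by comparison. What holds is narrower: dropping an event cannot raise any count in the table, so absolute counts in the affected group can only be understated. Even the severity mix is not pushed one way, because dropping an ungraded event that was in truth mild raises the severe share among the subjects shown.

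This is a minor correction, worth making because it is cheap and removes a stated rule that can produce a wrong count.

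**What to change.** In SAP Section 9.2.3, replace the exclusion with a Missing intensity category. Add it as a column in Table 1.6.5 and as a row in both intensity blocks of Table 1.6.1.1 and its subgroup versions (Tables 1.6.1.2 to 1.6.1.13). Place a subject in Missing only when none of that subject's AEs at the level shown is graded. Define Total in the footnote as all subjects with any AE at that level, so that it agrees with Table 1.6.2.1. Keep the listing as planned.

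This follows the convention in Section 6, and the laboratory shift shell in Table 1.7.1.2 already carries a Missing row and column. Counting missing intensity as severe is not recommended: it would report severe events that no investigator graded, and the Missing category reconciles the tables without that assumption.

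The cost is a revised sentence, four panels of Table 1.6.5, and the overview shell with its twelve subgroup versions. Section 7.1 says that derivations follow the individual study SAPs and that changes to study algorithms are not planned. Those SAPs are not available here, so small differences from the individual study tables are possible and should be footnoted. If no intensity is missing, the reported numbers do not change.

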9.2.4 Serious Adverse Events

The seriousness of an AE should be assessed by the investigator independently from the intensity of the AE. A SAE is any AE occurring at any dose that:

- results in death;
- is life-threatening (subject is at immediate risk of death at the time of the event);
- requires inpatient hospitalization or results in prolongation of existing hospitalization;
- results in persistent or significant disability/incapacity;
- is a congenital anomaly/birth defect in the offspring of a subject who received study drug; or
- is a significant or important medical event, i.e., an event that, based upon appropriate medical judgment, may jeopardize the subject and may require medical or surgical intervention to prevent one of the above mentioned criteria.

SAEs will be summarized by treatment/analysis group and listed.

9.2.5 Adverse Events Leading to Treatment Discontinuation

Any AEs collected with an investigational product action taken of "Study drug discontinued" will be summarized by treatment/analysis group.

9.2.6 Adverse Events Leading to Study Drug Dose Reduction

Adverse events leading to a study drug dose reduction will be summarized by treatment/analysis group. Events leading to study drug dose reductions will be identified as events having an investigational product action taken response of "Other" with a "Specify" value indicating a study drug dose reduction.

9.2.7 Adverse Events Leading to Death

Any AEs leading to death will be listed.

9.2.8 Adverse Events of Special Interest

Adverse events of special interest are grouped into three event categories: Neuropsychiatric (CNS), Falls, and Hallucinations. The CNS category combines the following SOCs: Nervous system disorder and Psychiatric disorder. The Falls category combines all PTs that contain the term "Fall" or "Falls". The Hallucinations category combines all PTs that contain the term "Hallucination".

Event incidence will be summarized treatment/analysis group.

Time to onset will be analyzed and is defined as the number of days from the first dose of study drug to the onset of the first AE in the category. Subjects will be censored at the latest date known not to have had such AE. The median time to event and the associated 95% confidence interval for the Placebo and 340 mg ADS-5102 treatment groups will be estimated using the Kaplan-Meier method. Kaplan-Meier estimates of the survival function will be calculated and displayed graphically.

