7.5 Subgroup Definitions

The following subgroups will be explored for key safety analyses:

- Gender
- Age ($<65, \ge 65, \ge 65$ to $<75, \ge 75$)
- Race (white, non-white)
- Baseline renal function (estimated GRF \leq 60 or estimated GFR \geq 60)
- Weight (< or \ge median)
- Baseline MAO-B inhibitor medications (Yes, No)
- Baseline Dopamine Agonist medications (Yes, No)
- Baseline levodopa dose (< or ≥ median)
- Time since PD diagnosis in years (< or \ge median)
- Age at PD diagnosis (< or \ge median)
- Prior Deep Brain Stimulation (Yes, No)
- Geographic Region (European Union vs North American)

For subgroups categorizations based on median values, a value for each treatment/analysis group will be calculated and subjects will be categorized separately for each treatment/analysis group in which they are included.

7.6 Definitions of Baseline, Analysis Day 1, and Study Day 1

The baseline assessment will be the last available assessment prior to the first dose of study medication for a particular treatment. For subjects receiving multiple treatments, baseline assessments will be defined for each treatment assignment. For subjects receiving 340 mg ADS-5102 in more than one study, the following logic will be applied to assign the baseline value:

- For subjects continuing into ADS-AMT-PD302 with no gap in treatment prior to enrollment, the baseline assessment will be the last available assessment prior to the first dose of 340 mg ADS-5102 in any study.
- For subjects continuing in ADS-AMT-PD302 with a gap in treatment prior to enrollment, the baseline assessment will be the last available assessment prior to the first dose of 340 mg ADS-5102 in ADS-AMT-PD302. Assessments from the first study in which the subject enrolled will not be considered for assignment as baseline.

An overall baseline value will be determined and used in summaries were overall values are calculated and displayed. This value will be assigned following the same logic outlined previously, but study treatment will not be considered in the selection of this value.

Analysis Day 1 is defined as the date of the baseline visit. Subjects should be dispensed the study drug at the baseline visit and presumably take the first dose at bedtime on the same day. No Day 0 is defined. Negative study days indicate observations were obtained prior to treatment.

Study Day 1 is defined as the date of the first dose of study drug for the individual study in which the subject participated.

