7.7 Calculations Using Dates

The following conventions will be used to calculate analysis day for reporting purposes:

- Analysis Day = date of measurement analysis day 1 +1, if date of measurement is on or after analysis day 1.
- Analysis Day = date of measurement analysis day 1, if date of measurement is prior to analysis day 1.

Study day will be presented in applicable listings where the calculated analysis day of the measurement is negative due to the definition of baseline for rollover subjects with treatment gaps prior to enrollment in the open-label extension. The following conventions will be used to calculate study day for reporting purposes:

- Study Day = date of measurement study day 1 +1, if date of measurement is on or after study day 1.
- Study Day = date of measurement study day 1, if date of measurement is prior to study day 1.

8 Summary Population

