8.1 Disposition of Subjects

Disposition data from each study will be integrated, listed, and summarized for the Safety population.

A frequency table by treatment/analysis group and overall will include the number and percentage of subjects along with last available completion status.

A separate table will show the number (%) of subjects who withdrew and the primary reason for withdrawal, by treatment/analysis group and overall. The primary reasons of withdrawal reported by subjects will be presented in this table. The number (%) of subjects who discontinued study drug and the reason for early discontinuation will be summarized in a

separate table. Subjects may contribute more than one event to the summary table since it is possible for a subject to discontinue from more than one study. A footnote indicating the number of subjects with multiple study discontinuations will be included in the summary table.

The time to discontinuation of study drug will be analyzed. The time to discontinuation is defined as the number of days from the Analysis Day 1 date to the last dose of study drug for a particular treatment. Subjects will be censored if no early study drug discontinuation occurred. The median duration and the associated 95% confidence interval for each treatment group will be estimated using the Kaplan-Meier method (log-log transformation). Kaplan-Meier estimates of the survival function will be calculated and displayed graphically.

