	XXXXX	340mg ADS-5102	XX	X	X	X • X
XXXXX-XX-XXX	XXXXX	260mg ADS-5102	XX	X	X	X • X
XXXXX-XX-XXX	XXXXX	420mg ADS-5102	XX	X	Х	X • X

Listing 2.4 Prior and Concomitant Medications Safety Population

Subject Identifier	Study Identifier	Treatment	ATC TERM/ PREFFERED TERM/ MEDICATION REPORTED	Indication	Start Date/ Stop Date/ Flag ¹	Dose/ Unit/ Route/ Frequency
XXXXX-XX-X-XXX	XXXXX	Placebo	XXXXXXXXXXXXX/ XXXXXXXXXXXXXXXXXX/ XXXXXX	XXXXXXXXX	DDMMMYYYY/ Ongoing/ P	XXXXX/ XXXXXX/ XXXXXXX
XXXXX-XX-XXX	XXXXX	340mg ADS-5102	XXXXXXXXXXXXXX/ XXXXXXXXXXXXXXXXXXXXXX	XXXXXXXXX	DDMMMYYYY/ DDMMMYYYY/ P/C	XXXXX/ XXXXXX/ XXXXXX/ XXXXXX

Note: Freq = Frequency

Prior medications are defined as medications taken within the 30 days that started and stopped prior to Analysis Day 1 (first day of study drug administration).

¹P=Prior medication, C=Concomitant medication

Prior and concomitant medications were coded with the WHO Drug dictionary dated MAR 2014.

Listing 2.6.1 Adverse Events Safety Population

Subject Identifier	Study Identifier	Treatment	System Organ Class/ Preferred Term/ VERBATIM TERM	Start Date (Day)/ Stop Date (Day)/ Duration (Days) ¹	Serious/ Intensity/ Causality/ Outcome/ Action Taken
XXXXX-XX-X-XXX	xxxxx	Placebo	XXXXXXXXXXXXXXXXXX/ XXXXXXXXXXXXXXXXXX	DDMMMYYYY (xx)/ DDMMMYYYY (xx)/ XX	Yes/ Mild/ Not Related/ Recovered/Resolved/ Dose not changed
XXXXX-XX-XXX	XXXXX	340mg ADS-5102	XXXXXXXXXXXXXXXXX/ XXXXXXXXXXXXXXXXX/ XXXXXX	DDMMMYYYY (xx)/ DDMMMYYYY (xx)/ XX	No/ Moderate/ Related/ Recovered/Resolved with sequelae/ Drug Interrupted
xxxxx-xx-xxx	XXXXX	260mg ADS-5102	XXXXXXXXXXXXXXXXX/ XXXXXXXXXXXXXXXX/ XXXXXX	DDMMMYYYY (xx)/ DDMMMYYYY (xx)/ XX	Yes/ Severe/ Not Related/ Unknown/ Drug Withdrawn
xxxxx-xx-xxx	XXXXX	420mg ADS-5102	XXXXXXXXXXXXXXXXX/ XXXXXXXXXXXXXXXXXXX	DDMMMYYYY (xx)/ DDMMMYYYY (xx)/ XX	No/ Mild/ Related/ Not Recovered/Not resolved/ Other
xxxxx-xx-xxx	XXXXX	340mg ADS-5102	XXXXXXXXXXXXXXXXX/ XXXXXXXXXXXXXXXXX XXXXXX	DDMMMYYYY (xx)/ DDMMMYYYY (xx)/ XX	Yes/ Severe/ Not Related/ Fatal/ Dose not changed

¹Duration (Days = Stop date - Start date + 1). Adverse events are coded using MedDRA Version 17.0.

<DIRECTORY PATH>PROGRAM NAME Executed: DDMMMYYYY hh:mm

Listing 2.6.2

Adverse Events Leading to Study Drug Dose Reduction

Safety Population

Same layout as X.X

¹Duration (Days = Stop date - Start date + 1). Adverse events are coded using MedDRA Version 17.0.

<DIRECTORY PATH>PROGRAM NAME Executed: DDMMMYYYY hh:mm

Listing 2.6.3

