- Figure 3.6.3.3 Kaplan-Meier Analysis of Time to Onset of AE (Hallucinations) by Age Safety Population
- Figure 3.6.3.4 Kaplan-Meier Analysis of Time to Onset of AE (Hallucinations) by Race Safety Population
- Figure 3.6.3.5 Kaplan-Meier Analysis of Time to Onset of AE (Hallucinations) by Baseline Renal Function Safety Population
- Figure 3.6.3.6 Kaplan-Meier Analysis of Time to Onset of AE (Hallucinations) by Weight Safety Population
- Figure 3.6.3.7 Kaplan-Meier Analysis of Time to Onset of AE (Hallucinations) by Baseline MAO-B Inhibitor Medications Safety Population
- Figure 3.6.3.8 Kaplan-Meier Analysis of Time to Onset of AE (Hallucinations) by Baseline Dopamine Agonist Medications Safety Population
- Figure 3.6.3.9 Kaplan-Meier Analysis of Time to Onset of AE (Hallucinations) by Baseline Levodopa Dose Safety Population
- Figure 3.6.3.10 Kaplan-Meier Analysis of Time to Onset of AE (Hallucinations) by Time since PD Diagnosis in Years Safety Population
- Figure 3.6.3.11 Kaplan-Meier Analysis of Time to Onset of AE (Hallucinations) by Age at PD Diagnosis Safety Population
- Figure 3.6.3.12 Kaplan-Meier Analysis of Time to Onset of AE (Hallucinations) by Prior Deep Brain Stimulation Safety Population
- Figure 3.6.3.13 Kaplan-Meier Analysis of Time to Onset of AE (Hallucinations) by Geographic Region Safety Population

Figure 3.1
Kaplan-Meier Analysis of Time to Study Drug Discontinuation
Safety Population

[figure not shown]

Analysis Day is the number of days since Analysis Day 1 + 1. Subjects will be censored if study drug was not discontinued at or before the last contact. Source Data: Listing 2.1.3, Table 1.1.3

<DIRECTORY PATH>PROGRAM NAME Executed: DDMONYYYY HH:MM

Programming note: All treatment/analysis groups will be presented.

 $\mbox{Figure 3.6.1.1} \\ \mbox{Kaplan-Meier Analysis of Time to Onset of AE (Neuropsychiatric)} \\ \mbox{Safety Population}$

[figure not shown]
The Neuropsychiatric category combines the following System Organ Classes: Nervous system disorder and Psychiatric disorder. Analysis Day is the number of days since Analysis Day 1 + 1. Subjects will be censored at their last contact date if no AE (Neuropsychiatric) occurred. Source Data: Listing 2.6.1, Table 1.6.10.2

<DIRECTORY PATH>PROGRAM NAME Executed: DDMONYYYY HH:MM

Programming note: Only Placebo and 340mg ADS-5102 will be presented.

[figure not shown]

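### Time-to-onset curves for special-interest AEs do not end follow-up at a treatment switch, so placebo subjects who roll over stay in the placebo risk set while on ADS-5102

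*SAP*

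**What the plan says.** **Time origin.** SAP 9.2.8 groups adverse events of special interest into neuropsychiatric events, falls and hallucinations. For each group, time to onset is "defined as the number of days from the first dose of study drug to the onset of the first AE in the category", and Kaplan-Meier curves are drawn for placebo and for 340 mg ADS-5102. The figure footnotes (Figure 3.6.1.1 onward) label the axis differently: "Analysis Day is the number of days since Analysis Day 1 + 1".

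**Censoring.** In the text of 9.2.8, a subject without an event is censored at the latest date on which he or she was known to be free of it. In the notes to Table 1.6.10.2 and its companions, and in the figure footnotes, the date is that of last contact. None of these refers to last dose or to a change of treatment.

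**Definitions elsewhere.** In SAP 7.6, "Analysis Day 1 is defined as the date of the baseline visit". For a subject who took 340 mg in more than one study with a gap before PD302, "the baseline assessment will be the last available assessment prior to the first dose of 340 mg ADS-5102 in ADS-AMT-PD302". Section 7.7 foresees that in listings the "calculated analysis day of the measurement is negative due to the definition of baseline for rollover subjects with treatment gaps prior to enrollment". Section 8.1 measures time to drug discontinuation "from the Analysis Day 1 date to the last dose of study drug for a particular treatment".

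**Who can switch.** SAP 7.2 lets one subject appear in more than one treatment group. The footnote to SAP 11.2 shows that PD301 completers could continue into the open-label extension. Protocol 6.3 gives ADS-5102 to everyone in PD302.

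**The concern.** A subject randomized to placebo who later enters PD302 has a last contact date inside PD302. Under the stated censoring rule, that date ends the subject's time on the placebo curve. The placebo risk set can thus hold people who are between studies, off any study drug, and people who are taking ADS-5102.

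Placebo is the only comparator for these three event groups, and each group has an overall curve and 12 subgroup versions. A reader comparing late placebo incidence with 340 mg incidence would take the tail of the placebo curve as placebo experience, when none of it is.

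There is a smaller question of origin. The wording in 9.2.8 does not say the first dose of which treatment. For 340 mg gap subjects, no rule says what happens in the curve to events from the earlier study, which carry negative Analysis Days.

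**Working it through.** The SAP states no event count, rate or median for these curves, so there is no planned figure to reproduce.

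**1. Rules side by side.**
- Discontinuation curve (8.1): event time runs to last dose of the particular treatment.
- Onset curves (9.2.8 and notes): follow-up runs to last event-free date or last contact, with no treatment named.
- Events: 7.2 assigns treatment from the individual studies, and Listing 2.6.1, the source for the onset tables, shows study and treatment for each event. A PD302 event would be listed under ADS-5102.

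Together, the last two attribute events by treatment but do not end follow-up by treatment.

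**2. How long a placebo subject can stay on the placebo curve.**
- Placebo dosing in PD301 (SAP 3): 25 weeks; 25 × 7 = 175 days. In AM201 it is 8 weeks, 56 days.
- PD302 (Protocol 6.6): up to 101 weeks; 101 × 7 = 707 days, then follow-up 2 weeks later, 14 days.
- PD301 subject rolling over without a gap: 175 + 707 + 14 = 896 days, of which 721/896 = 80% follows the switch.
- If data stopped at SAP issue (assumption; the freeze date is not given): 14 July 2014 to 13 November 2015 is 487 days; 175 + 487 = 662 days, of which 487/662 = 74% follows the switch.
- With a 2-week follow-up window for placebo (the PD302 window, assumed to apply), placebo-attributable time ends at 175 + 14 = day 189.

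**3. Illustration of the effect on the placebo curve.** All rates here are assumptions.
- Arm sizes: 83/4, about 21, from AM201 and 126/2 = 63 from PD301.
- Placebo event rate 0.006 per week; 10% dropout; 50% or 80% of completers roll over; AM201 gap 26 or 104 weeks.
- PD302 event rate 0.03 per week for 4 weeks, then 0.004 per week.

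Kaplan-Meier incidence over 3,000 simulated runs:

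| Rule | Week 25 | Week 30 |
|---|---|---|
| Censoring limited to treatment plus window | 13.8-14.0% | 14.7-15.0% |
| Last contact, PD302 events not placebo events | 12.2-12.9% | 12.3-13.3% |
| Last contact, PD302 events counted as placebo | 12.2-12.9% | 19.1-19.4% |

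At week 30, nobody is at risk under the first rule; 30 to 53 subjects are under last-contact censoring.

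Hand check of the first row: 1 - exp(-0.006 × 25) = 13.9%, and 1 - exp(-0.006 × 27) = 15.0% once the 2-week window is included.

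Hand check of week 25 in the other rows, ignoring PD301 dropout and earlier events. From week 10 to week 25, AM201 rollovers are held at risk although off drug. They number 21 × 0.9 × 0.5 = 9.45 to 21 × 0.9 × 0.8 = 15.12, beside 63 PD301 subjects. The placebo share of the risk set is 63/72.45 = 0.870 to 63/78.12 = 0.806. Cumulative hazard is 0.006 × 10 + 0.006 × 15 × 0.870 = 0.138, or 0.133 with 0.806, giving incidence of about 12.9% or 12.4%.

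The two last-contact rows then part because PD301 rollovers either cannot have a placebo event or bring in the early PD302 rate.

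**4. Origin.** For a subject in one study the two origins agree to within about a day: 7.6 expects subjects to "presumably take the first dose at bedtime on the same day". For 340 mg gap subjects, 9.1 defines exposure from Analysis Day 1, while the Table 1.5 note defines it from the first dose date and restricts gap subjects to PD302. The Listing 2.4 note also equates Analysis Day 1 with the first day of dosing. These point to the PD302 dose as the intended origin. What remains open is the treatment of first-study events: for a completed AM201 course, all 56 dosing days precede Analysis Day 1, and 7.7 deals with that only in listings.

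**The case against.** **Attribution by treatment implies a limit.** Section 9 summarizes by treatment or analysis group, and Listing 2.6.1 carries the treatment for each event. This largely answers which events belong to placebo, and it makes the contaminated version (about 19% at week 30) the less likely reading. It does not answer who is at risk. A subject whose events can no longer count, but who stays in the denominator, lowers the estimate.

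**The study SAPs may settle it.** SAP 7.1 defers derivations to them and lets algorithm changes be documented later. They are not available here, and the PD302 SAP may well address gaps. A placebo curve that continues into PD302 arises only on pooling, so this plan is the place to end it.

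**The contrast with 8.1 is partial.** Section 8.1 ties the event time to a particular treatment but gives no censoring date, and the Figure 3.1 footnote also mentions last contact. That is fair: 8.1 shows that per-treatment wording was available, not that a complete rule exists elsewhere.

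**A stronger reading of the origin.** A reader might infer that text and footnotes set two rival clocks, one running from the first dose ever across the off-drug gap, and that the 340 mg curves would differ materially. The documents do not support that. Section 9.1, the Table 1.5 note and the Listing 2.4 note treat first dose and Analysis Day 1 as the same, and Table 1.5 uses PD302 alone for gap subjects. Any size put on such a difference would also rest on gap counts and gap lengths that are not given.

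**The effect is small and descriptive.** At the assumed rates the likelier reading costs about 2 percentage points, and no test is planned. That limits the priority of the point without removing it.

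**Conclusion.** The censoring defect stands and should be fixed. As written, the placebo curve can extend to day 896, or day 662 if data stop at SAP issue, with at most 175 days of placebo treatment behind it. With a 2-week window, everything after day 189 is non-placebo time.

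The direction of the error depends on event attribution: downward if PD302 events are assigned to ADS-5102, as 7.2 and Listing 2.6.1 imply, and contaminated by active-drug events if they are not. The day counts follow from the documents. The percentages rest on assumed event, dropout and rollover rates, which the documents do not give, and whether any median would change cannot be determined.

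The origin point is secondary: an unqualified first dose in 9.2.8 and a missing rule for first-study 340 mg events of gap subjects. It should not be read as proof of two conflicting 340 mg curves.

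A reader might also infer that the adverse event incidence tables are wrong. They use no follow-up time and are unaffected.

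**What to change.** In 9.2.8, the table notes and the figure footnotes, state one set of rules:

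- **Origin:** Analysis Day 1 for the treatment being summarized.
- **Gap subjects on 340 mg:** start at PD302, consistent with 7.6 and Table 1.5, and leave first-study time and events out of the curve. Those events stay in the incidence tables.
- **Events:** count only those with onset in that treatment's period, including its follow-up window.
- **Censoring:** the earliest of last contact, the end of that follow-up window, and first dose of the next treatment. Moving from 340 mg in PD301 to 340 mg in PD302 without a gap is not a change of treatment.

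The cost is SAP wording and minor derivation code, with no new data. The downside is small: a few gap subjects' first-study events leave the curves.
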